3.5.5.5 Safety Analysis

Safety and tolerability will be assessed by clinical review of all relevant parameters including DLTs, other AEs, laboratory tests, ECG measurements, and vital signs.

DLTs will be listed. At the end of the trial, a dose-response relationship for the rate of experiencing a DLT in Cycle 1 will be estimated using the pooling-of-adjacent-violators algorithm. This dose-safety estimation will be used to support determination of the MTD. The dose-response relationship, overall tolerability and safety profile, and the PK and PD data will inform the determination of a recommended Phase 2 dose.

Note: As of Amendment 11, PK analyses will not be performed (see Section 3.3.2).

The 80% confidence intervals and Bayes credible intervals for DLT and drug-related toxicity rates in Cycle 1 for an identified MTD level will be provided. Summary statistics (median and range) for time to onset of first drug-related toxicity in each dose level will be provided. Adverse experiences will be summarized as counts and frequencies for each dose level. Laboratory assessments, vital signs, and other safety endpoints will be summarized as appropriate.

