1.5 SAMPLE

A total of approximately 1137 eligible patients will be enrolled in this study, with approximately 28 patients in Part A, approximately 506 patients in Part B, approximately 35 patients in Part C, approximately 88 patients in Part D, and approximately 480 patients in Part F. (A total of 1260 patients were enrolled in the study; 32 patients in Part A, 564 patients in Part B, 41 patients in Part C, 104 patients in Part D, and 519 patients in Part F).

In Part A, patients with any type of carcinoma may be enrolled, and patients may have non-measurable disease. Patients in Part A will be distributed as follows:

- Dose escalation = 10 patients
- Part A-1 (PK expansion at MTD) (up to 10 mg/kg Q2W): 6 patients
- Part A-2 (PK expansion, intra-patient dose escalation, Q3W): 12 patients

In Part B, only patients with MEL may be enrolled (metastatic MEL or patients with locally advanced disease and not candidates for surgical resection or a definitive local therapy), and patients must have measurable disease (see Section 2.2 and Appendix 6.5). Part B will enroll approximately 506 patients distributed as described in [Table-1-1](#).

Table-1-1

Patient Distribution in Part B

	10 mg/kg	2 mg/kg
Ipilimumab Naïve	61 ^{1,3}	15 ^{2,3}
Ipilimumab Treated	40 ^{1,3}	0 ³
Ipilimumab Refractory	80 ^{2,3}	80 ^{2,3}
Ipilimumab Naïve or Treated	230 ^{1,4}	
1 Includes patients with dosing schedules of Q2W and Q3W. 2 Dosing schedule is Q3W 3 Up through Amendment 001-06 4 Amendment 001- 07		

Enrollment of patients at 2 mg/kg who are naïve to ipilimumab in Part B will begin once all 10 mg/kg patients in Part B are enrolled up through Amendment 04. All patients enrolled after the approval of Amendment 03 or approval of the administrative memo dated 06-Jan-2012, will be dosed Q3W with the exception of patients enrolled under Amendment 07.

Enrollment of the first 13 patients in Part B will be restricted to ipilimumab-naïve patients (which will serve as basis for the first interim analysis). The remaining patients will be enrolled without a hold to complete a total of 60 patients (40 ipilimumab-naïve and 20 ipilimumab-treated). With Amendment 04, an additional 55 patients

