With Amendment 10 tumor imaging will be performed approximately every 16 weeks (112 days) (± 28 days) from the first dose of study medication through Year 3, and then Q6 months (24 weeks) (± 28 days) through Years 4 and 5. After 5 years, imaging will be performed annually or per institutional standard of care. Response status will be assessed by the study site. Refer to Section 3.3.1.3 of the protocol for additional information. The same imaging technique must be used in a patient throughout the study. After first documentation of response or progression, repeat imaging will be required approximately 4 weeks later for confirmation, as per immune related response criteria (irRC) guidelines (see Appendix 6.5), (see Section 2.4.1).

Part B

Part B will only enroll patients with MEL. Pembrolizumab (MK-3475) will be administered at 2 mg/kg and 10 mg/kg. The dosing interval to be used in Part B for patients who consent under protocol Amendment 02 will be repeated Q2W. These patients will continue Q2W dosing until they discontinue study therapy. For patients consented under Amendments 03, 04, 05, 06, or following approval of the administrative

memo dated 06-Jan-2012, dosing will be Q3W. Patients consented under protocol Amendment 07 will be administered 10 mg/kg at either Q2W or Q3W.

It is expected that Part B will enroll approximately 506 patients, including 76 ipilimumab-naïve patients: approximately 61 patients at 10 mg/kg; and 15 patients at 2 mg/kg. Part B will also include approximately 40 patients who had previously received ipilimumab (at 10 mg/kg), approximately 80 patients who are ipilimumab refractory at 2 mg/kg Q3W and 80 patients who are ipilimumab refractory at 10 mg/kg Q3W. Amendment 07 will enroll approximately 115 additional patients at 10 mg/kg Q2W and another 115 patients at 10 mg/kg Q3W irrespective of their prior ipilimumab status (i.e., ipilimumab naïve or previously treated). The first 13 patients enrolled in Part B will be required to be ipilimumab-naïve.

Tumor Assessment in Part B

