Data from Part B was presented at the Society of Melanoma Research in November 2012. Safety analysis on 132 patients revealed most adverse events to be grades 1-2. The most commonly reported AEs were fatigue (28%), nausea (23%), rash (22%), diarrhea (20%) and cough (19%). The most commonly reported drug-related AEs were fatigue (22%), rash (18%), diarrhea (14%), pruritus (14%), and arthralgia (11%). Of note, pneumonitis (all Gr 1-2) was noted at a rate of 3% amongst patients with melanoma. Grade 3-5 AEs occurred in 27% of patients, of which 9% were considered drug-related. Of note, preliminary safety data from patients with NSCLC appears similar to that in melanoma, with the exception that the rate of pneumonitis is about 8%. Preliminary efficacy analyses on the first 85 malignant melanoma patients that were dosed with pembrolizumab (MK-3475) revealed an objective response rate (confirmed + unconfirmed) of 51% by irRC (immune related response criteria) and 47% by RECIST. Confirmed responses amongst all major NSCLC histologies have been observed in Part C.

Two recent Phase III studies of the anti-CTLA4 mAb ipilimumab have shown statistically significant improvement of overall survival in patients with stage IV melanoma [71, 72]. At the same time, the BRAF inhibitor vemurafenib has shown significant survival improvement compared to chemotherapy with DTIC in patients with stage IV melanoma harboring mutant BRAF [73]. Despite that encouraging progress, melanoma patients overall outlook remains bleak, and the development of new agents is warranted to further improve clinical outcome benefit. Based on the preliminary clinical data, PD-1 inhibitors such as pembrolizumab (MK-3475) appear to be attractive candidates for pursuing that goal.

An important objective of the present study is the investigation of biomarkers in tumor tissue which may be able to identify which melanoma and NSCLC patients have a high probability to benefit from treatment with pembrolizumab (MK-3475) and which do not. Therefore, Parts B, C, D and F of the study will mandate pretreatment tumor biopsies.

The study will also collect tumor biopsies while on treatment and post treatment, as changes in biomarkers compared to baseline may provide meaningful insights into characteristics associated with sensitivity or resistance to pembrolizumab (MK-3475).

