3.5.4.2 Safety Analysis

The All Patients as Treated (APaT) population will be used for the analysis of safety data in this study. The APaT population consists of all patients who received at least 1 dose of study treatment.

In order for a patient to be considered evaluable for the analysis of DLT, the patient must have either had a DLT in Cycle 1 or had received at least 90% of the prescribed dose of pembrolizumab (MK-3475) in Cycle 1 and completed all safety evaluations up to and including at least 28 days after the first administration of pembrolizumab (MK-3475) without experiencing a DLT. A patient without a DLT will be replaced if he/she did not adequately complete the evaluation period associated with the first cycle of study therapy (i.e., discontinued prematurely due to a reason unrelated to study therapy) or if that patient received <90% of the prescribed dose.

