3.5.8 Subgroup Analyses and Effect of Baseline Factors

In assessment of anti-tumor activity in melanoma population, patients will be analyzed by treatment history with ipilimumab and by dose level and dosing interval (Q2W or Q3W). In addition, ipilimumab-naïve patients in Part B will be combined with those in Part D for a sensitivity analysis of treatment difference between the two doses. In assessment of anti-tumor activity in NSCLC populations in Part C and Part F, patients will be analyzed by line of therapy and by dose level.

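### The only adverse-event layout Section 3.5.5.5 states is by dose level, which mixes 51% NSCLC at 10 mg/kg with 22% at 2 mg/kg and can make a tumour-type difference look like a dose effect

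*Combined protocol and SAP*

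**What the plan says.** Section 3.5.5.5 (Safety Analysis): "Adverse experiences will be summarized as counts and frequencies for each dose level". The same paragraph gives time to onset of first drug-related toxicity by dose level. It names no split by tumour type, study part or schedule.

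Section 3.5.4.2: "The All Patients as Treated (APaT) population will be used for the analysis of safety data in this study". That population is every patient who received at least one dose.

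Section 3.5.8 does separate the populations, but for efficacy: "In assessment of anti-tumor activity in NSCLC populations in Part C and Part F, patients will be analyzed by line of therapy and by dose". For melanoma it adds ipilimumab history and dosing interval, again for anti-tumour activity.

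Section 3.1.2 reports pneumonitis in 3% of melanoma patients, from a safety analysis of 132 patients, and then says that "preliminary safety data from patients with NSCLC appears similar to that in melanoma, with the exception that the rate of pneumonitis is about 8" per cent.

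Section 1.3 states the safety objectives part by part: melanoma in Parts B and D, NSCLC in Parts C and F. Safety is also the first primary objective in Section 2.1.1. The opening of Section 3.5 says that no separate SAP will follow.

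**The concern.** Dose was not assigned independently of tumour type. Most planned NSCLC patients are at 10 mg/kg, and most planned 2 mg/kg patients have melanoma. A by-dose table of all treated patients therefore compares two different tumour mixes.

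Pneumonitis is the one event for which the protocol itself reports a difference between the tumour types. Section 3.1.2 also records drug-related pneumonitis deaths with another anti-PD-1 antibody, so readers will look at that row.

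Two things are at stake. A reader may take a difference in tumour mix for a dose effect. And the table would not answer objectives that ask for the safety profile in melanoma and in NSCLC separately. Efficacy is to be reported for each population and by dose and schedule (Section 3.5.5.1); the safety section has no matching provision.

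**Working it through.** **Reproducing the plan's totals.** "A total of approximately 1137 eligible patients will be enrolled in this study" (Section 1.5). The cohort sizes in Sections 1.5 and 2.4.1 give:

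- Part B: 61 + 15 + 40 + 80 + 80 + 230 = 506.
- Part F: 88 + 32 + 280 + 40 + 40 = 480.
- Total: 28 (Part A) + 506 + 35 (Part C) + 88 (Part D) + 480 = 1137, as stated.

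The Part B inputs include "approximately 61 patients at 10 mg/kg; and 15 patients at 2 mg/kg" (ipilimumab-naïve) and "approximately 80 patients who are ipilimumab refractory at 2 mg/kg Q3W and 80 patients who are ipilimumab refractory at 10 mg/kg Q3W".

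**NSCLC share by dose.** Part A is left out because its tumours are mixed.

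| Planned dose | Melanoma | NSCLC | Total | NSCLC share |
|---|---|---|---|---|
| 10 mg/kg | 61 + 40 + 80 + 230 + 44 = 455 | 35 + 88 + 32 + 280 + 40 = 475 | 930 | 51.1% |
| 2 mg/kg | 15 + 80 + 44 = 139 | 40 (F-3) | 179 | 22.3% |

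**Crude pneumonitis rate with no dose effect.** Rate = (melanoma n × 3% + NSCLC n × 8%) / total.

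- 10 mg/kg: (13.65 + 38.00) / 930 = 5.55%.
- 2 mg/kg: (4.17 + 3.20) / 179 = 4.12%.
- Difference 1.44 points; ratio 1.35.

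Equivalently, the shift is the rate gap times the gap in NSCLC share: 5 points × (0.511 − 0.223) = 1.44 points. Within tumour type, the same assumptions give 3% against 3% and 8% against 8%, so the shift disappears.

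**Visibility against sampling error.**

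- Standard error of the difference: √(0.0555 × 0.9445/930 + 0.0412 × 0.9588/179) = 1.66 points.
- Chance that 10 mg/kg shows the higher crude rate: Φ(1.44/1.66) = about 81%.
- Chance of two-sided p < 0.05, with a pooled standard error of 1.83 points under the null: Φ((1.44 − 1.96 × 1.83)/1.66) = about 10%.

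**Sensitivity to the rates (assumed values).** At 3% and 6% the shift is 0.9 points; at 2% and 10% it is 2.3 points; at 1% and 10% it is 2.6 points.

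**Sensitivity to the cohort sizes.**

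- Sections 3.5.5.4 and 3.5.7 give 250 randomised F-2 patients instead of 280. The 10 mg/kg share becomes 49.4% and the shift 1.35 points.
- Adding Part A patients to 10 mg/kg (10 or all 28, tumour type assumed) gives shares of 49.6% to 51.6%.
- Table 2-1 as printed gives 61.5% against 27.2% and 1.7 points. Its rows sum to 442 for Part B and 631 for Part F, against 564 and 519 enrolled in Section 1.5. Adjusting to those totals, with an assumption about which rows change, gives about 50% to 57% against 27% and 1.1 to 1.5 points.

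**Schedule.** All 179 planned 2 mg/kg patients are Q3W. At 10 mg/kg, 115 (Part B, Amendment 07) + 44 (F-1) + 112 + 40 (F-2) = 311 of 930 are Q2W. A further 61 + 40 = 101 Part B patients were on either schedule, so 311 is a minimum. The documents give no adverse-event rates by schedule, so this part cannot be sized.

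**Randomised contrasts in the plan.**

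- 2 against 10 mg/kg: 160 (ipilimumab-refractory) + 88 (Part D) = 248 patients, all melanoma.
- Q2W against Q3W at 10 mg/kg: 230 + 88 + 280 = 598 patients (568 if F-2 is 250).
- NSCLC at 2 mg/kg: F-3, a single arm of 40.

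**The case against.** The strongest reply is that the plan does not exclude tables by tumour type. The by-dose sentence does not claim to be exhaustive. Section 1.3 sets safety objectives by part, Section 3.2.5.6 plans a Part B lock covering safety and efficacy, and Section 3.1.2 already reports pneumonitis separately for the two tumours. A reader might infer that the sponsor will pool everything and conceal the tumour difference; the documents do not support that. What stands is narrower: reporting by tumour type is suggested by the objectives but specified nowhere.

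A second reply is that the sentence sits among text on dose-limiting toxicity and the maximum tolerated dose, and so is Part A language. It is not limited to Part A, and Section 3.5.3.2 has adverse events evaluated in all parts. If it were limited to Part A, the SAP would state no adverse-event layout for 1137 − 28 = 1109 planned patients.

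A third reply is that the artefact is small, the table is descriptive, and no between-dose test of adverse events is planned. This is right as far as it goes. The inputs are also fragile: 3% of 132 is about 4 cases, and the NSCLC figure is preliminary with no denominator. But the shift is systematic, and it does not shrink as patients are added in the same proportions.

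Finally, a reader might infer that the randomised cohorts settle the dose question. They do not for NSCLC: no planned randomised cohort there compares 2 with 10 mg/kg, and Table 2-1 shows only 6 and 5 first-line patients at those doses on Q3W under Amendment 06. In melanoma, 124 per arm at 3% gives about 4 pneumonitis cases per arm.

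**Conclusion.** The point holds as a should-change of modest size. The one stated layout mixes 51% NSCLC with 22% NSCLC, merges Q2W with Q3W at 10 mg/kg, and does not match the tumour-specific safety objectives.

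On the protocol's own rates, tumour mix alone gives about 5.6% against 4.1% pneumonitis. It is tempting to say that this will appear as a dose effect. The figures do not support that: the shift is below its standard error and would reach nominal significance about one time in ten. It can mislead, and it would favour the claimed direction in about four trials of five.

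The misdescription does not depend on sampling error. Under these rates, NSCLC patients at 2 mg/kg would be represented by 4.1%, about half of 8%, and melanoma patients at 10 mg/kg by 5.6% instead of 3%.

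The size rests on planned cohort sizes with Part A excluded, on preliminary pneumonitis rates, and on the assumption of no dose or schedule effect within tumour type.

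**What to change.** In Section 3.5.5.5:

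- Tabulate adverse events, adverse events of special interest and time to onset by tumour type within originally assigned dose and schedule. Using the original assignment gives each patient one column despite the change of regimen under Amendment 10.
- Keep the pooled by-dose table, described as an overall summary and not as a dose comparison.
- Base the main safety contrasts on the randomised cohorts: 2 against 10 mg/kg in the ipilimumab-refractory cohort and Part D, and Q2W against Q3W in Part B (Amendment 07), F-1 and randomised F-2.
- Show the NSCLC 2 against 10 mg/kg comparison through F-3, labelled as non-randomised. Leaving it out would remove essentially all dose information in the tumour with the higher reported pneumonitis rate.

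The enrolment counts in Table 2-1 and Section 1.5 should be reconciled first, since they set the denominators.

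The tables use data already collected. The cost is more columns with smaller cells, so rates for uncommon events will be imprecise.

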3.5.6 Multiplicity

A Hochberg procedure will be applied to final analysis of RR and DCR for internal decision purposes based on the ipilimumab-naïve patients treated at 10 mg/kg in Part B enrolled through Amendment 4. The overall type I error rate is set at 5% (one-sided),

i.e., the trial is considered to have reached the efficacy objective if the two corresponding p-values for testing the null hypothesis (RR=10% and DCR=30%) are less than 5% OR either one is less than 2.5%. There are two planned interim analyses for administrative purposes. There is no intention to terminate the study early for efficacy, and no multiplicity adjustment is applied to the interim analyses.

The predictive biomarker hypothesis on concordance between tumor volume change and PD-L1 will be formally tested at a type I error rate of 2.5% (one-sided) separately for each part of the study, irrespective of the outcome from efficacy analyses. Once the null hypothesis is rejected, a step-down procedure may be applied to the testing of other biomarker hypotheses prospectively specified before the end of the study. While additional exploratory analyses will be conducted to evaluate alternative predictive biomarkers, there is no multiplicity control of such analyses and no formal conclusion can be made.

The efficacy hypothesis on anti-tumor activity of pembrolizumab (MK-3475) is tested at 5% (one-sided) for Part B ipilimumab-treated (non-randomized), at 10% (one-sided) for Part C, and at 2.5% (one-sided) for all other populations. Between-dose comparisons are all conducted at 20% (two-sided), or equivalent 10% (one-sided) for sample size and power calculation purpose below, except for Part B (10 mg/kg Q3W vs 10 mg/kg Q2W) which is conducted at 5% (two-sided).

3.5.7 Sample Size and Power Calculations

Part B ipilimumab-naïve enrolled through Amendment 4 (non-randomized)

With 61 ipilimumab-naïve patients treated at the 10 mg/kg in both Q2W and Q3W, the study has approximately 97% power to detect an effect size of RR=25% or DCR=50% under the null hypothesis of RR=10% and DCR=30%, or >99% power to detect an effect size of RR=30% or DCR=55%, at a type I error rate of 5% (one-sided) based on the Hochberg procedure. For the subgroup of patients on a dose /schedule, the corresponding powers to the two effect sizes are respectively 87% and 97% when the sample size is 40, 76% and 91% when the sample size is 30, and 44% and 62% when the sample size is 15.

Part B ipilimumab-treated enrolled through Amendment 4 (non-randomized)

With 40 patients treated at 10 mg/kg, the study has approximately 92%/98% power to rule out a $\leq 5\%$ spontaneous RR (null hypothesis) when the true RR is 20%/25% at the 5% type I error rate (one-sided). With true RR assumed to be 20%/25%, the corresponding power is 75%/90% when sample size is 30 and 59%/78% when sample size is 20 at Q3W or Q2W.

Part B ipilimumab-refractory enrolled after Amendment 04 (randomized: 10 mg/kg Q3W vs 2 mg/kg Q3W)

With 80 ipilimumab-refractory patients at each dose level, the study has ~85% (or 96%) power to detect a 15% (or 20%) difference in RR between the two doses at the 10%

type I error rate (one-sided) when the RR in the inferior arm is 10%. A p-value of 10% approximately corresponds to a 7% empirical difference in RR.

In addition to detecting dose response, we are also interested in testing whether pembrolizumab (MK-3475) is superior to putative chemotherapies in this population. While the spontaneous RR is likely less than 5%, there is no historical data on response rate of chemotherapies in the ipilimumab-refractory population. However, it ranged from 5% to 10% for chemotherapies in three recently completed phase 3 studies (ipilimumab in 1st line melanoma patient, and trametinib and vemurafenib in patients with BRAF V600E mutation). Therefore, it is reasonable to use 10% as the null hypothesis for testing the anti-tumor activity of pembrolizumab (MK-3475) against putative chemotherapies in this population. With 80 patients treated at a dose level, the study has 93% power to reject the null hypothesis at a type I error rate of 2.5% (one-sided) when the true response rate of pembrolizumab (MK-3475) is 25%. A p-value of 2.5% approximately corresponds to a 19% empirical response rate when sample size is 80. With the prevalence of high PD-L1 projected to be from 40% to 60%, the number of high PD-L1 patients treated at a dose level ranges from 32 to 48 and the half-width of the 95% confidence intervals for RR at a dose level approximately ranges from 14% to 17% when the empirical RR in the high PD-L1 group is 50% and from 13% to 16% when the empirical RR in the high PD-L1 group is 70% or is 30%. With 32 to 48 patients in the PD-L1 high group, the study has 79% to 94% power to reject the null hypothesis of 10% RR at type I error rate of 2.5% (one-sided) when the true RR is 30%.

Part C NSCLC (single arm)

With 35 NSCLC patients treated at RP2D, the study has approximately 80% power to rule out a $\leq 9\%$ RR (null hypothesis) when the true RR is 22% at the 10% type I error rate (one-sided).

Part D ipilimumab-naïve enrolled after Amendment 04 (randomized)

With 44 patients treated at 2 mg/kg and 44 treated at 10 mg/kg, the study has 80% power to detect 30% vs. 10% or 90% power to detect 25% vs 5% in RR between the two dose levels at the 10% type I error rate (one-sided). A p-value of 10% approximately corresponds to a 12% empirical difference in RR.

With 44 patients treated at a dose level, the study has 89% power to test the null hypothesis of RR=10% at 2.5% type I error rate (one-sided) when the true RR is 30%. A p-value of 2.5% approximately corresponds to an empirical RR of 23% (10/44).

Based on preliminary data from the non-randomized patients, the RR appears similar between the ipilimumab-refractory population and the ipilimumab-naïve population. A pooled analysis of the PD-L1 high patients from Part B (randomized) and Part D (randomized) will be conducted. It is expected that 50 to 75 PD-L1 high patients will be treated at a dose level in the pooled analysis. With this sample size, the study has >95%

power to reject the null hypothesis of 10% RR at type I error rate of 2.5% (one-sided) when the true RR is 30%.

Part B enrolled after Amendment 04 (randomized: 10 mg/kg Q3W vs 10 mg/kg Q2W)

A total of approximately 230 patients will be randomized 1:1 to 10 mg/kg Q3W or 10 mg/kg Q2W, stratified by ipilimumab-naïve vs non ipilimumab-naïve. Based on preliminary data from non-randomized patients, the RR appears similar between the non ipilimumab-naïve population and the ipilimumab-naïve population. The primary analysis of this cohort is based on a pooled analysis, stratified by ipilimumab treatment history. Subgroup analyses will also be conducted. With 230 patients, the study has ~85% power to detect a 20% difference (i.e., 30% vs 50%) in RR between the two doses at the 2.5% type I error rate (one-sided). A p-value of 2.5% approximately corresponds to a 13% empirical difference in RR.

Similar to randomized cohorts in Part B and Part D between 10 mg/kg Q3W vs 2 mg/kg Q3W, anti-tumor activities of pembrolizumab (MK-3475) at a dose schedule as well as related to PD-L1 expression will also be investigated.

Part F NSCLC 1L PD-L1 positive (randomized)

With 44 patients per dose level, the study has 86% power to detect a 25% difference in RR (i.e., 45% vs 20%) at $\alpha=10\%$ (1-sided) between two dose levels. A p-value of 10% approximately corresponds to a 13% empirical difference in RR.

With 44 1L patients treated at a dose level, the study has 91% power to test the null hypothesis of $RR=25\%$ at 2.5% type I error rate (one-sided) when the true RR is 50%. A p-value of 2.5% approximately corresponds to an empirical RR of 41% (18/44).

Part F NSCLC 3L+ (single arm)

With 32 3L+ patients treated at 10 mg/kg, the study has 90% power to test the null hypothesis of $RR=10\%$ at 2.5% type I error rate (one-sided) when the true RR is 35%. A p-value of 2.5% approximately corresponds to an empirical RR of 25% (8/32).

Part F NSCLC 3L+ PD-L1 negative (single arm)

With 40 patients treated at 10 mg/kg Q2W, the study has >90% power to rule out a >30% RR if <8 patients respond (i.e., probability of observing < 8 responses is <10% when true RR is 30%).

Part F NSCLC 2L+ PD-L1 positive (single arm)

With 40 patients treated at 2 mg/kg Q3W, the study has ~90% power to test the null hypothesis of RR =10% at 2.5% type I error rate (one-sided) when the true RR is 30%. A p-value of 2.5% approximately corresponds to an empirical RR of 22.5% (9/40).

Part F NSCLC 2L+ PD-L1 positive (randomized)

Approximately 250 patients will be randomized (3:2) to 10 mg/kg Q3W and 10 mg/kg Q2W. The randomization may be stratified by PD-L1 expression level based on a preliminary cutoff point once available (see Section 3.5.5.4 for details). With 250 patients, the study has approximately 95% power to detect a 15% difference in RR between the two doses at type I error rate of 10% (one-sided) assuming that the RR at 10 mg/kg Q3W is 10%.

Enrollment of patients with weakly positive tumors will be capped at 50% so that at least 75 patients with strongly positive tumors will be treated at 10 mg/kg Q3W. With 75 patients treated at 10 mg/kg Q3W, the study has 85% power to detect a 15% difference in RR between pembrolizumab (MK-3475) and historical control which is conservatively estimated to be 15% (i.e., 30% vs 15%) at type I error rate of 2.5% (one-sided). A p-value of 2.5% approximately corresponds to an empirical RR of 25% (i.e., the lower bound of the 95% CI for an empirical RR at 25% will exclude 15%). With 50 patients at 10 mg/kg Q2W, the study has 68% (or 89%) power to detect a 15% (or 20%) difference in RR between pembrolizumab (MK-3475) and historical control at type I error rate of 2.5% (one-sided). A p-value of 2.5% approximately corresponds to an empirical RR of 28% (i.e., the lower bound of the 95% CI for an empirical RR at 28% will exclude 15%). If 10 mg/kg Q2W has comparable anti-tumor effect to 10 mg/kg Q3W in the population, the two doses will be pooled for a joint analysis as appropriate. Regardless, if the primary analysis in the biomarker strongly positive population is positive a step-down analysis will be performed to assess all biomarker positive patients including patients with weakly positive tumors.

If Part F data show no evidence that line of therapy (1L vs 2L+) impacts efficacy, data will be combined across line of therapy and within dose for more powerful assessment of difference in RR between the two dose schedules and for more precise estimation of RR at a dose schedule. The pooled analysis will be conducted in the overall biomarker positive population as well as in the strongly biomarker positive population, as appropriate.

PD-L1 biomarker effect

Kendall's tau statistic will be used for testing the PD-L1 biomarker effect for various tumor and treatment groups. All testing will be conducted at type I error rate of 2.5% (one-sided). For a sample size of approximately 45 patients with both post-treatment disease assessments and valid evaluation of baseline PD-L1 expression levels in newly obtained tumor biopsies, the study has approximately 90% power to detect a one-fold

difference in concordance (i.e., odds of concordance relative to discordance = 2, or in other words tumor is twice more likely to reduce than to increase if the patient's tumor has high expression of the PD-L1 than low expression). When the sample size is reduced to 25 patients, Kendall's tau has 90% power to detect a 1.5 to 2-fold difference in concordance. In addition, the Youden index and other methods will be used for biomarker cut-off point analysis.

